This proposed study is a prospective 12-week tobacco cessation trial using established methods and outcomes typical of tobacco cessation trials, but specifically recruiting co-users of cannabis to; 1) evaluate the impact of co-use on tobacco cessation (compared to tobacco only users), and 2) assess changes in cannabis use during tobacco treatment. Adult tobacco users (ages 18-40; N=208) who are motivated to quit smoking will be recruited. Cannabis co-users will be oversampled (2:1). All participants will receive a first-line tobacco cessation pharmacotherapy (varenicline) paired with a behavioral intervention to bolster abstinence (contingency management and psychosocial counseling) for 12 weeks, while cannabis use will not be specifically addressed. Biochemical verification and self-reports (through mobile daily diaries) of substance use will be collected throughout treatment. A subset of cannabis-tobacco co-use participants (N = 48) will engage in an additional ecological momentary assessment (EMA) portion of the study (EMA supplement) for granular observation of patterns of co-use.

Specific Aims of the proposed research are:

Aim #1: examine the impact of cannabis co-use on tobacco cessation among co-users compared to tobacco only users.

Hypothesis 1: Co-users will have lower rates of 7-day point prevalence abstinence from tobacco at the end of treatment (Week 12) compared to tobacco only users.

Aim #2: Among co-users, assess changes in cannabis use during tobacco cessation treatment.

Hypothesis 2: Co-users with moderate to high severity of nicotine dependence will demonstrate increases in concurrent cannabis use, while lower severity of nicotine dependence will yield no changes in cannabis use.

Exploratory Aim: To assess for a dose-dependent impact of cannabis use severity on tobacco cessation outcomes among co-users.

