B1. Study Overview. This proposed prospective tobacco cessation study will evaluate the impact of concurrent cannabis use and severity on tobacco abstinence among co-users and assess changes in cannabis use during treatment. Adult tobacco users (ages 18-40) who are motivated to quit smoking will be recruited. Cannabis co-users will be oversampled (2:1) and will be compared to tobacco only participants (using appropriate propensity score models). All participants will receive first-line tobacco cessation pharmacotherapy (varenicline) paired with a behavioral intervention to bolster abstinence rates (contingency management and psychosocial counseling) for a standard 12-week treatment period. Cannabis use will not be targeted with treatment. This is not a treatment outcome study per se and thus we are not evaluating (with a control group) an intervention. Rather, cannabis use status (co-use vs. not) is our independent variable. Biochemical verification of tobacco and cannabis use will be collected at screening and throughout the 12-week treatment period in addition to daily self-reports of use. Specifically, this study will: 1) examine the impact of cannabis co-use on tobacco cessation among co-users compared to tobacco only users (Aim #1); 2) with the use of frequent measurement, assess changes in cannabis use (among co-users) during tobacco treatment and determine if profiles of changes in cannabis use emerge (i.e., compensatory use, reduction, no change) (Aim #2); and 3) assess for a dose-dependent impact of cannabis use severity on tobacco cessation outcomes among co-users (Exploratory Aim).

It should be noted that while this is not a randomized and blinded study (cannabis co-use status will be known to research staff), it is important to not bias the results of the study. The hypothesis is that cannabis co-use will adversely impact tobacco cessation, but it's important to the scientific integrity of this study to obscure that hypothesis from study participants and manage biases with research staff. Staff will be educated about introducing bias into the study and methods to manage bias in non-randomized and non-blinded trials. For research participants, the aim of the study will intentionally broad and ambiguous to not

overtly influence their behavior and tobacco quit attempt. The title of the study and consent document, therefore, are not as specific as they would normally be to maintain the integrity of this research.

B2. Preliminary Studies.

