3.0 Study Endpoints

Below is a table of the study endpoints and outcomes.

Type	Name	Time Frame	Brief Description
Primary	7-day point prevalence tobacco abstinence at the end of treatment (Week 12)	Final 7 days of treatment (Week 12)	7-day point prevalence abstinence from tobacco at the end of treatment (Week 12) will be assessed via biochemical verification and participant self-report and rates of abstinence will be compared between cannabis co-users and tobacco only controls.
Secondary	Changes in cannabis use during tobacco cessation treatment (among co-users)	Final 4 weeks of study treatment (Weeks 8-12)	Among cannabis co-users, cannabis use rates and amounts during the final 4 weeks of tobacco treatment (Weeks 8-12) will be assessed and

			nicotine dependence will be the primary model predictor.
Other: Exploratory	Cannabis co-use severity on tobacco cessation (among co-users)	Throughout trial participation	Tobacco abstinence and indicators of tobacco reduction (average cigarettes per day, quantitative cotinine, etc.) throughout the trial will be examined as a function of baseline cannabis use severity (determined by days of use in the past 30) to assess for dose-dependent impact on tobacco outcomes based on cannabis use severity.

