10.0 Statistical Analysis and Data Management

Analytic Strategy.

Power and sample size. The proposed study is powered to detect a meaningful difference in end of treatment tobacco abstinence between cannabis co-users and tobacco only users. Secondarily, the study will assess the relationship between cannabis use patterns during treatment and nicotine dependence severity in co-users. Specific Aim #1: Examine the impact of cannabis co-use on tobacco cessation outcomes among co-users compared to tobacco only users. Hypothesis 1: Co-users will have lower rates of 7-day point prevalence abstinence from tobacco at the end of treatment (Week 12) compared to tobacco only users. In a cross-sectional survey of national household data (51), tobacco cessation was reported among 65.5% of respondents who endorsed no cannabis use as compared to 21.8% of tobacco cessation in those reporting current cannabis use ($\Delta=43\%$). Studies examining the efficacy of varenicline for tobacco cessation (108, 109) noted near 50%-point prevalence abstinence at treatment conclusion (Week 12) in the varenicline-treated group. Finally, in our recently completed adolescent varenicline trial (U01 DA0317779), youth cannabis co-users reported point prevalence tobacco abstinence in 20% of participants at Week 12 and 43% in those who use tobacco only (analysis with all available data). The proposed R01 study intends to apply a successful tobacco treatment (varenicline) paired with contingency management in treatment-seeking smokers. Assuming a similar abstinence rate in tobacco only users (45%) and a successful abstinence rate in participants who are cannabis co-users as compared to the adolescent study (20%; $\Delta=25\%$), to achieve 80% power with a 5% type 1 error rate, a sample of 82 participants in the cannabis co-using cohort and 41 in the tobacco only cohort. However, to account for the inclusion of 2 study sites in the design, an additional fixed factor of site will be included in the analytic models. Although we hope that equal proportions of co-users and non co-users present at each site, we understand that the fundamental differences between the Charleston metro area, Pickens County SC, and Florence exist and may cause some correlation between co-use group and study site. Assuming that the proportion of variance in co-use groups due to study site and other covariates may be moderate ($R^2=0.25$) and that attrition will not exceed 25%, we have adjusted our study sample size to account for this scenario. This increases our randomized sample to a total of 208 (139 cannabis co-users and 69 tobacco only users) accounting for both site correlations with co-use group and anticipated attrition. If site correlations with study outcomes or attrition are lower than pre-specified, our statistical power will exceed 80%. Specific Aim #2: Among co-users, assess changes in cannabis use during tobacco cessation treatment. Hypothesis 2: Co-users with moderate to high severity of nicotine dependence will demonstrate increases in concurrent cannabis use, while lower severity of nicotine dependence will yield no changes in cannabis use. To attain adequate power to assess Aim #2, a within co-use cohort comparison, the study will oversample the cannabis co-use cohort as compared to the tobacco only cohort (2:1). At screening, nicotine dependence will be assessed via the Fagerström Test for Nicotine Dependence (FTND) (92) and categorized accordingly: low nicotine dependence (0-4), medium or high nicotine dependence (5-6; 7-10). Cannabis use during the final 4 weeks of study treatment as compared to baseline use will be assessed among co-users. Based on our preliminary data from an ongoing adult tobacco cessation trial (R34 DA042228), we have nearly equivalent numbers of participants falling into low and moderate/high nicotine dependence categorizations (Mean=4.5; Median=5). Therefore, we anticipate ~40% will have medium/high nicotine dependence. With 208 participants, 139 in the cannabis co-use cohort (104 completers), we will achieve 80% power with a type 1 error rate of 5% to detect a between group cannabis use difference of Cohen's $d\approx0.6$ (Med/High nicotine dependence vs. low nicotine dependence).

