Primary Study Aims: Aim 1: To assess the difference in the log-odds of abstinence from tobacco at the end of treatment (Week 12) between baseline cannabis co-users compared to tobacco only participants, augmented inverse probability weighted logistic regression models will be developed. The inverse of the conditional probability of being in the cannabis co-use cohort will be included in the model to account for inherent imbalances between study groups and to reduce bias by resembling a randomized controlled trial. In addition to the inverse propensity weights, AIPW methods incorporate a covariate and study site adjusted model for the study group outcome (114). Aim 2: To assess the association of baseline nicotine dependence severity (Med/High nicotine dependence vs. low nicotine dependence) with cannabis use rates during study treatment, generalized linear mixed effects models will be assessed with cannabis use rates and amounts during the final 4 weeks of treatment as the primary indicator of cannabis use severity and nicotine dependence group as the primary model predictor. In addition to grouping by nicotine dependence severity, continuous levels of dependence severity (FTND score) will be modeled to assess possible linear and quadratic relationships between dependence severity and cannabis use. Following examination of the differences in end of treatment cannabis use rates based on baseline nicotine dependence, rates of cannabis use will be assessed by group (nicotine dependence severity) over all weekly study visits to determine if those with increased dependence severity exhibit a different trajectory (slope and pattern) of cannabis use during the entire study treatment. Model-based means and associated standard errors will be used to test group level differences. Exploratory Aim: To assess the relationship between baseline cannabis use severity and tobacco outcomes, generalized linear mixed effects models will be developed with weekly 7-day point prevalence abstinence from tobacco as the primary model outcome. In addition to tobacco abstinence, weekly average cigarettes per day will be examined as an indicator of use reduction differences over time. Longitudinal patterns in tobacco abstinence and use amounts will be modeled through the inclusion of baseline cannabis use severity indicators, study visit, and baseline tobacco use rates as model covariates. Additionally, differential effects over time will be examined with the inclusion of the interaction of cannabis use severity and study visit. Model-based means and associated standard errors will be used to test group level differences across the study treatment.

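### The primary Aim 2 model compares cannabis use at the end of treatment between dependence groups, but Hypothesis 2 is about change from baseline

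*Combined protocol and SAP*

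**What the plan says.** Four places frame Aim 2 as change in cannabis use:

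- Section 1.0, Hypothesis 2: "Co-users with moderate to high severity of nicotine dependence will demonstrate increases in concurrent cannabis use", with no change expected at lower dependence.
- Section 2.0, B1 Study Overview: the study will "determine if profiles of changes in cannabis use emerge (i.e., compensatory use, reduction, no change".
- Section 3.0, name of the secondary endpoint: "Changes in cannabis use during tobacco cessation treatment (among co-users".
- Section 10.0, Power and sample size: "Cannabis use during the final 4 weeks of study treatment as compared to baseline use will be assessed among co-users".

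The two places that define what is measured and modelled do not carry this through. The endpoint description in Section 3.0 says that "cannabis use rates and amounts during the final 4 weeks of tobacco treatment (Weeks 8-12) will be assessed". The Aim 2 model under Primary Study Aims in Section 10.0 has "cannabis use rates and amounts during the final 4 weeks of treatment as the primary indicator of cannabis use severity" and uses dependence group as the main predictor. Neither mentions baseline cannabis use.

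The same paragraph does name baseline terms for the Exploratory Aim: "baseline cannabis use severity indicators, study visit, and baseline tobacco use rates as model covariates".

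Baseline cannabis data are collected. Section 9.0 has a 30-day timeline follow-back (TLFB) at screening. Daily diaries start before medication, from screening according to the Screening Visit text and one week before Day 0 according to the Mobile sessions text.

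**The concern.** A baseline term for Aim 2 is unstated rather than excluded. But an analyst who follows the model paragraph, and sees baseline terms listed for the Exploratory Aim and none for Aim 2, would fit a comparison of end-of-treatment levels.

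Dependence groups within the co-use cohort are not randomised, and the propensity weighting in Section 10.0 addresses co-users versus tobacco-only users, not these groups. Section 2.0, A2 reports that cannabis use is associated with greater nicotine dependence, so a gap before medication is plausible. If there is one, a difference in final levels may simply be that gap, or a gap in the other direction may hide a real rise. No comparison of levels between groups addresses the second half of Hypothesis 2, that use in the low-dependence group does not change.

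**Working it through.** **Inputs from Section 10.0, Power and sample size.** 139 co-users; attrition 25%, so 139 × 0.75 = 104 completers; about 40% with medium/high dependence, so 42 versus 62; 80% power; 5% type 1 error (taken as two-sided; the plan does not say). That paragraph also states that "we have nearly equivalent numbers of participants falling into low and moderate/high nicotine dependence categorizations", so a 52/52 split was checked too.

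**Assumptions not in the documents.** The baseline gap g between groups (SD units), whether it persists, and the correlation rho between baseline and end-of-treatment use. A normal two-sample t test with equal SDs stands in for the mixed model.

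**1. The plan's own figure.** The standard error in SD units is sqrt(1/42 + 1/62) = 0.200. The detectable difference is (1.960 + 0.842) × 0.200 = 0.560, or 0.565 by noncentral t. This agrees with the stated value of about 0.6. At exactly 0.6 the power is 84.5%. The power figure is sound; the issue is what is being compared.

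**2. Level test when nobody changes and the gap persists.** Noncentrality = g / 0.200, df = 102.

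| Gap (SD) | 0 | 0.2 | 0.3 | 0.4 |
|---|---|---|---|---|
| Rejects, 42/62 | 5.0% | 16.8% | 31.8% | 50.9% |
| Rejects, 52/52 | 5.0% | 17.3% | 32.9% | 52.4% |

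**3. Three analyses at an assumed gap of 0.3 SD (42/62).** The SD of change is sqrt(2(1 − rho)); the residual SD after baseline adjustment is sqrt(1 − rho²).

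- *Gap persists, nobody changes.* The level test is off by 0.3, the covariate version by 0.3(1 − rho), the change contrast by 0.
- *Gap shrinks to 0.3 × rho (regression toward a common mean).* The level test is off by 0.3 × rho, the change contrast by 0.3(1 − rho), the covariate version by 0.

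| Rejection at rho = 0.3 / 0.5 / 0.7 | Level | Change contrast | Baseline covariate |
|---|---|---|---|
| Gap persists | 32 / 32 / 32% | 5 / 5 / 5% | 19 / 14 / 10% |
| Gap shrinks | 7 / 12 / 18% | 14 / 12 / 9% | 5 / 5 / 5% |

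Simulation with 8,000 runs per case agrees to within one percentage point. The level test exceeds 5% in both situations; each baseline method holds 5% in one.

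**4. Masking.** If only the medium/high group rises, by 0.6 SD, but it starts 0.3 SD lower, the final difference is 0.3 SD. The power of the level test is then 31.8%, against 84.5% with no gap. This direction runs against the association cited in Section 2.0, A2.

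**5. Precision for the no-change prediction.** The 95% half-width for within-group change is t × sqrt(2(1 − rho)/n).

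| rho | 0.3 | 0.5 | 0.7 |
|---|---|---|---|
| Low group, n = 62 | ±0.30 SD | ±0.25 SD | ±0.20 SD |
| Medium/high group, n = 42 | ±0.37 SD | ±0.31 SD | ±0.24 SD |

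**6. Detectable difference at 80% power, in final-period SDs.** Level: 0.565 at any rho. Change contrast: 0.565 × sqrt(2(1 − rho)) = 0.67, 0.57, 0.44. Baseline covariate: 0.565 × sqrt(1 − rho²) = 0.54, 0.49, 0.40 (rho = 0.3, 0.5, 0.7).

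**The case against.** The strongest reply is that the plan already says it. The power paragraph is in the same section and states the baseline comparison, and the endpoint is named as a change. That is true, and it makes this a mismatch rather than an absence. But the model paragraph and the endpoint description are what an analyst will implement, and they do not repeat it.

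Second, the Aim 2 text goes on to compare trajectories by dependence group over the weekly visits, and with a quit date on Day 8 the first week is largely pre-quit. This gives real protection against reading a stable gap as change. It is a follow-on to the primary comparison, though, and names no pre-medication point. The Secondary Data Analysis paragraph also plans trajectory models and an analysis of change in co-users, but ties neither to dependence group.

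Third, Section 3.0 defines baseline cannabis severity by days of use in the past 30. That is a candidate baseline, but it is given for the exploratory endpoint only.

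Fourth, the Aim 2 model is described as assessing an association with use during treatment, and for that question a level comparison is correct. It is then not a test of Hypothesis 2.

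Fifth, the rejection rates rest on assumed gaps; with no gap the level test holds 5%. This stands, and the figures should be read only as illustrations.

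Sixth, a change contrast is not always better. If the gap shrinks and rho is 0.3 it rejects in 14% of trials against 7% for the level test, and baseline adjustment is more precise at every rho shown. This also stands, and is why both versions should be reported.

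**Conclusion.** The concern holds. The hypothesis, the endpoint name and the power paragraph are about change; the primary Aim 2 model and the endpoint description give only levels in the final 4 weeks. As written, that test cannot show an increase in one group or the absence of change in the other. This conclusion needs no assumed number.

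The size of the consequence does rest on assumptions. For persisting gaps of 0.2 to 0.4 SD with no change in anyone, false rejection is 17% to 51% instead of 5%; the true gap, its direction, its persistence and rho are unknown. The matter concerns the secondary endpoint and should be corrected before analysis. Aim 1 is not affected.

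**What to change.** Align Section 3.0 and the Aim 2 model in Section 10.0 with the power paragraph:

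- Add pre-medication cannabis use to the primary Aim 2 mixed model, preferably as a baseline time point with a contrast of dependence group by period (final 4 weeks minus baseline), because the hypothesis is about change.
- Report change within each dependence group with a 95% confidence interval, and judge the no-change prediction by that interval, not by a non-significant p-value.
- Name one source and window as the main baseline, and use the other as sensitivity. The lead-in diaries match the instrument used in treatment; the screening TLFB is closer in length to the final 4 weeks. If diaries are chosen, reconcile their two stated start points.
- Show the baseline-covariate (ANCOVA) version beside the change contrast, since the two rest on different assumptions about how a gap behaves.
- Keep the weekly trajectory analysis as supportive.

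The cost is SAP wording and one added model time point, with no new data. The downsides are that the change contrast is less precise than the level test when rho is below 0.5 (0.67 against 0.57 SD detectable at rho 0.3), and that it rejects too often if a gap regresses toward the mean (14%, 12% or 9% at an assumed 0.3 SD gap and rho of 0.3, 0.5 or 0.7).

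### Hypothesis 2 predicts change within each nicotine-dependence group, but the Aim 2 tests that are specified and powered are contrasts between the groups

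*Combined protocol and SAP*

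**What the plan says.** Hypothesis 2 has two parts, given in Section 1.0 and again under Power and sample size in Section 10.0. The first is "Co-users with moderate to high severity of nicotine dependence will demonstrate increases in concurrent cannabis use". The second is "lower severity of nicotine dependence will yield no changes in cannabis use". Each describes change over time inside one dependence group.

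The Aim 2 paragraph under Primary Study Aims in Section 10.0 uses "cannabis use rates and amounts during the final 4 weeks of treatment as the primary indicator of cannabis use severity", with "nicotine dependence group as the primary model predictor". The FTND score is then fitted as a linear and quadratic term. A model over the weekly visits follows, "to determine if those with increased dependence severity exhibit a different trajectory (slope and pattern) of cannabis use during the entire study treatment". Finally, "Model-based means and associated standard errors will be used to test group level differences".

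The power statement matches these analyses: with 139 co-users (104 completers), "we will achieve 80% power with a type 1 error rate of 5% to detect a between group cannabis use difference" of Cohen's d about 0.6, medium/high versus low dependence.

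Change is not absent from the plan:
- The same power paragraph says: "Cannabis use during the final 4 weeks of study treatment as compared to baseline use will be assessed among co-users".
- Section 2.0, B1 (Study Overview) hopes to distinguish compensatory use, reduction and no change.
- Section 3.0 names the secondary endpoint as change in cannabis use.
- The Secondary Data Analysis text in Section 10.0 plans trajectory groups and a look at changes in the co-use group as a whole.

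None of these specifies a test or estimate of change from baseline by dependence group. The Aim 2 model paragraph names no baseline term. No margin is given for the no-change claim, and no rule says which result supports Hypothesis 2.

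**The concern.** A contrast between two groups fixes only the difference between their changes. It cannot tell a rise in the medium/high group with a flat low group from a flat medium/high group with a fall in the low group, or from a fall in both. Nor can it detect a rise that both groups share. The second half of the hypothesis is a claim of absence, which a non-significant result does not establish.

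The missing baseline term adds to this. If the outcome is the unadjusted level of use in the final four weeks, the contrast is not even a contrast of changes. A baseline difference between dependence groups could produce a significant result with no change in either group.

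The scientific premise in Section 2.0 (A4) treats compensatory cannabis use as a possible harm of successful cessation. The direction of change in the medium/high group is therefore the question that Aim 2 exists to answer.

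**Working it through.** **Inputs.** From Section 10.0: 139 co-users, attrition of 25%, about 40% medium/high, alpha 5%, 80% power. Assumptions: two-sided tests, and changes expressed in SD units of change with the same SD in both groups. The documents do not give that SD.

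**Group sizes.** 139 × 0.75 = 104.25, so 104 completers. 40% of 104 is about 42 medium/high, leaving 62 low.

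**The plan's own figure.** SE of the contrast = √(1/42 + 1/62) = 0.200 SD. Detectable d = (1.960 + 0.842) × 0.200 = 0.56 (0.565 with the t distribution). This agrees with the stated value of about 0.6 and confirms that the powered test is the between-group contrast.

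**Power of the contrast at 0.6 SD.** Φ(0.6/0.200 − 1.96) = Φ(1.04) = 0.85. Only the difference enters the formula, so every pair of true changes 0.6 SD apart gives the same answer.

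**Scenarios.** Normal changes with SD 1, 40,000 simulated trials each. The entries are percentages of trials.

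| True change: medium/high, low | Contrast significant, medium/high above low | Increase shown in medium/high (n=42) | Low group within ±0.40 SD (n=62) |
|---|---|---|---|
| +0.6, 0 (both claims true) | 84.8 | 96.9 | 85.8 |
| 0, −0.6 (both claims false) | 84.4 | 2.6 | 0.1 |
| −0.3, −0.9 (both groups fall) | 84.4 | <0.1 | <0.1 |
| +0.9, +0.3 (both groups rise) | 84.2 | 100 | 19.2 |
| +0.6, +0.6 (equal rise) | 2.5 | 96.9 | 0.1 |

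**What within-group tests can do at the planned size.**
- Medium/high, n=42: detectable change at 80% power = 2.80/√42 = 0.43 SD (0.445 with the t distribution). Power is 48% for a true change of 0.30 SD, 72% for 0.40 and 97% for 0.60.
- Low, n=62: the 90% CI half-width is 1.645/√62 = 0.21 SD. With a true change of zero, two one-sided tests at 5% have power of 24% for a margin of ±0.25 SD, 51% for ±0.30, 72% for ±0.35, 86% for ±0.40 and 98% for ±0.50.
- Both together, with true changes of +0.6 and 0 and a margin of ±0.40 SD: about 83%. Requiring the contrast as well: about 75%.

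**Sensitivity to the split.** The preliminary median FTND quoted in Section 10.0 is 5, which already falls in the medium category, so the split could be nearer equal. At 52 versus 52 the contrast has 86% power at 0.6 SD. The equivalence power in the low group becomes 77% at ±0.40 SD and 12% at ±0.25 SD.

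**The case against.** The strongest reply is that the plan does look at change. The power paragraph compares final-four-week use with baseline, B1 lists the three profiles that need to be separated, and the secondary analyses examine change and trajectories. A reader might infer from the Aim 2 paragraph that the groups are only ever compared with each other. The documents do not support that. What remains is that none of this text sets out change by dependence group, and none of it reaches the Aim 2 model.

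A reader might also infer that Hypothesis 2 would be declared supported with both halves false. No passage says that a significant contrast counts as support; the plan has no decision rule at all. Similarly, one might infer that a fall in the low group would be reported as compensation in the other group. The planned weekly rates by group, with model-based means and standard errors, would often show the direction. Misreading is possible but not built into the plan.

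The near-identical 85% figures follow by construction and say nothing about how likely each scenario is. That is fair: they show what the contrast cannot distinguish, not what will happen.

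Two further points stand. Within-group change is uncontrolled. Co-users enter on recent cannabis use (at least 10 of the past 30 days, or a positive urine test), so regression to the mean could pull change downward, and time trends common to both groups cancel in the contrast but not within a group. And a formal equivalence test for a secondary, non-randomised aim is one defensible standard; estimates with confidence intervals are another.

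**Conclusion.** The point holds as a mismatch between hypothesis and analysis. Hypothesis 2 is about change within each dependence group, while the inferences specified and powered for Aim 2 are contrasts between dependence levels. At the planned size a 0.6 SD difference is significant with about 85% probability whether the medium/high group rises or the low group falls, and an equal rise in both groups is significant in the predicted direction only 2.5% of the time.

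The percentages rest on 42 versus 62 completers, approximate normality, equal SD of change and two-sided 5% tests. The logical gap does not depend on them: unequal SDs would move the 85%, but it would still be the same for every pair of changes with the same difference. The calculation also takes the contrast to be one of changes, which the Aim 2 model paragraph does not secure.

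This should be changed, but it concerns a secondary endpoint and leaves the Aim 1 analysis untouched.

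**What to change.** In the Aim 2 analysis text:

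1. Include baseline cannabis use in the model, and pre-specify the model-based change from baseline to the final four weeks, with a 95% CI, in each dependence group.
2. Base the increase claim on the change in the medium/high group, and state its detectable size (about 0.43 to 0.45 SD at 80% power with 42 completers).
3. Keep the between-group contrast as the test of effect modification.
4. For the low group, choose one of two courses. Either report the CI and state that a non-significant change will not be read as no change, or fix and justify an equivalence margin in advance. The margin matters: ±0.25 SD would leave the test with little power at this sample size.
5. State which combination of results supports Hypothesis 2, and restate power for it.

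Alternatively, reword Hypothesis 2 as effect modification only and leave the tests as they are, with baseline use added to the model.

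The cost is SAP wording and two extra estimates from data and a model already planned. Hypothesis 2 becomes harder to meet, and the equivalence option needs a defended margin. The within-group changes must be reported as uncontrolled pre-post estimates, open to regression to the mean and common time trends, which is why the contrast should stay beside them.
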